D.3.8. Refinement of Fast-VESTAL and analyzing MEG data using conventional methods: L1-minimum types of solutions, including Fast-VESTAL, provide sparse solutions. It was shown that the high degree of spatial smoothing has an adverse effect on the positive detection rate of mTBI [1], which suggests that MEG source imaging methods with high spatial resolution (being sparse) may have unique advantages for mTBI. To systematically examine this topic, we will also analyze the MEG same data using conventional MEG source imaging techniques such as L2-minimum norm (MNE [105] and sLORETA [106] with non-sparse solutions), beamformer [107], conventional dipole fitting [38,39], as well as Champagne [108]). We will also refine Fast-VESTAL and further test its performance for 1) non-focal sources and 2) for deep sub-cortical sources.

D.4 Assessing Efficacy of IASIS Treatment using MEG Source Imaging in Veterans with mTBI (Aim 1)

D.4.1. IASIS Procedure: IASIS (Micro Current Neurofeedback [30]) is a 6-week (two 30-minute sessions per week) passive neurofeedback LIP-tES intervention with EEG monitoring. The IASIS device uses 5 EEG electrodes. The EEG interface device is the J&J Engineering I-330 C2, provided specifically for IASIS. The EEG sampling frequency is 256 Hz on each of 2 EEG acquisition channels. The feedback LIP-tES is delivered via the 4 EEG leads (A+, A-, B+, B-), with respect to the Common Neck Reference (isolated). During each session, 2 electrodes (A- and B-) are attached to the participant's left and right mastoids, while the remaining two electrodes (A+ and B+) are moved to various locations on the scalp to record EEG signals. All four (A+, A-, B+, B-) electrodes are involved in applying weak electric current pulses back to the brain (the feedback process). The feedback signal consists two types of narrow pulse trains, both with 150 mV in amplitude: A Type 1 pulse is 25 ms in duration and contains carrier waves at ~50 KHz. The repetition rate of Type 1 pulse train is fixed at 3.6 Hz (Fig. 5); A Type 2 pulse is 120 ns in duration and contains carrier waves at ~100 MHz. The repetition rate of Type 2 pulse train is in 2 Hz - 12.5 Hz range and determined dynamically by adding incremental frequencies specified in pre-programmed schedules to the dominant brainwave frequency (from EEG recordings). For example, IASIS first picks up the dominant brain rhythms (e.g., 3 Hz). Next, the feedback electrical pulses are sent back to the brain, with a repetition rate by adding incremental frequencies (e.g., 1 Hz, 2 Hz, etc.) to the dominant one, changing each 5 seconds throughout the 25-second-long protocol. According to the SR model, these feedback pulses potentiate endogenous slow-waves in the brain. A train of IASIS pulses with specific repetition rate will not only potentiate oscillation at that frequency, but also oscillations with lower frequencies. This process is similar to studies that used trains of electrical / magnetic pulses to potentiate oscillations at lower frequency than the pulse-train's repetition rate in animals and humans [68,109].

Moving A+ and B+ electrodes to various places may draw unnecessary attention from the participant to specific electrode sites. To avoid that, we prep and pre-place a set of electrodes on the scalp of the participant following the 10-20 EEG configuration. These 10-20 sites are the potential sites for the A+ and B+ electrodes. During the treatment sessions, the sites of A+ and B+ electrodes (selected from the pre-placed 10-20 configuration) will be switched by software without the participant's knowledge, so that the participant cannot tell which sites were activated. Out of the standard 10-20 electrode sites, electrode pairs activated were: F3/F4, C3/C4, P3/P4, O1/O2, T5/T6, Fz/Pz, FPz/Cz, FP1/FP2, F9/F10, F9/FC3. Each Schedule takes between 22-25 seconds per site and each Schedule is delivered twice per electrode pair.

D.4.2. Sham treatment and double-blind design: During the sham treatment, we will still prep and preplace the electrodes for common reference, A-, B-, plus the set of electrodes on the scalp of the participant following the 10-20 EEG configuration for A+ and A-, just like the procedure for real IASIS treatment. However, no LIP-tES pulses will be sent from the IASIS system during sham treatment, based a code entered to the system. A Staff Research Associate (SRA) #1 will assign a mTBI participant to either the mTBI-IASIS or the mTBI-Sham group, with an attached code from an existing IASIS code bank. Then, the IASIS treatment operator (SRA #2) who is blind to the group assignment will enter the code to the IASIS system during treatments. Based on the code, IASIS system automatically load the protocol for either IASIS or Sham treatment. Only at the end of the study (after Visit 16), the group assignment is revealed. Therefore, both the participant and IASIS treatment operator (SRA #2) are blind to the group assignment during the study.

D.4.3. IASIS's immediate effect of slow-wave potentiation -- pre- and post-session rs-MEG changes: To achieve this goal, we will perform three pairs of pre- and post-session rs-MEG exams at the beginning, midpoint, and the end of the IASIS treatment course: in Visit 3 for the 1st IASIS session (S1), Visit 9 for the 7th IASIS session (S7), and Visit 14 for the 12th IASIS session (S12). The post-treatment rs-MEG will be performed within 30 minutes immediately after the treatment session. Two-factor mixed-design repeated measures ANOVA with covariates, equivalent to linear mixed effect model, will be applied for statistical analysis. We will: 1) assess the within-subject significance of the immediate slow-wave potentiation due to IASIS session by comparing the voxel-wise Z-score and total abnormal MEG Z-scores between pre- and postsession exams; and 2) assess the between-group treatment effect by comparing IASIS with Sham. The total abnormal MEG Z-score is calculated by summing up the Z-score from all voxels that showed statistically significant slow-wave generation. The dependent variables at both time points are either voxel-wise Z-scores or total abnormal MEG Z-scores, and the predictors are time (pre- and post-session), group (IASIS versus Sham), and their interaction. Veterans receiving IASIS treatment but not sham are expected to show significantly increase rs-MEG slow-wave generation in post-session rs-MEG exam immediately after the treatment session (Hypothesis 2). The preliminary result in C.5 (Fig. 5) supports this hypothesis.

D.4.4. Ultimate slow-wave reduction following the IASIS treatment course -- pre- and post-treatment rs-MEG exams: Participants in mTBI-IASIS group will participate in the 6-week IASIS treatment, whereas those in mTBI-Sham group will participate in a sham treatment for the same time period. To assess the ultimate effect of the IASIS treatment course, the 1-week post-

treatment follow-up rs-MEG in Visit 15 will be compared with the baseline rs-MEG in Visit 2 (Fig. 10). The focus of our analyses are the pre- and post-IASIS change in the abnormal MEG slow-wave generation for both voxel-wise Z-score maps and the total abnormal MEG Z-scores. Two-factor mixed-design repeated measures ANOVA with covariates will be used to: 1) assess the within-subject treatment effect by comparing the voxel-wise Z-score and total abnormal MEG Z-scores between pre- and post-treatment exams; and 2) to assess the between-group treatment effect by comparing IASIS with Sham. Participants receiving IASIS treatment, but not sham, are expected to show significantly reduction in abnormal rs-MEG slow-wave generation in post- over pre-IASIS exams (Hypothesis 3). Preliminary result in C.6.2 and C.6.3 (Figs. 6B and 7) supports this hypothesis.

D.4.5. Assessing Efficacy of Nexalin Treatment on a Subset of Veterans with mTBI and remaining PCS after IASIS Treatment: Participants in the mTBI-IASIS group who have participated in the 6-week IASIS treatment and who mention they have persistent PCS in a follow-up phone interview will be offered Nexalin Treatment. Nexalin TES or Sham TES will be administered once per day, Monday through Friday. Participants will receive 10-20 treatments, 3-4 times a week for 4 weeks, or up to 5 times a week for 4 weeks. All procedures were performed at [name] office at VASDHS or at the UCSD RIL (prior to the move out of RIL) and were administered by Research Associates who will be specially trained on using the Nexalin equipment. Nexalin TES involves placing three conductive pads on the head (one on the forehead and one behind each ear). The patient then sits as the device administers the current through the pads. The waveform generated by the Nexalin device is a high frequency square wave (100 kHz), which has its amplitude modulated at a frequency of 4Hz, 40Hz, and 77.5 Hz. Amplitude of the waveform is controlled to range from **0 to 15 mA peak current**. Each treatment session will last for 60 minutes. The treatment is not expected to be painful, but some individuals may experience discomfort at the sites of the pad electrodes (i.e. tingling and burning). In most cases, patients cannot feel when the pads are activated. The Sham treatment will be identical with the exception that there will be no current through the electrodes. Since the Nexalin treatment is undetectable, this will exactly mimic active treatment. Pre-and post- MEG's will be administered. Also, the same questionnaires used during the IASIS treatments will be administered on a daily or weekly basis, depending on the questionnaire's instruction.

D.5 Study Changes in PCS and PTSD Severity due to IASIS (Aim 2)

We will study clinical symptom changes due to IASIS treatment. In both mTBI groups, RPQ and NSI will be used to assess PCS and their changes due to IASIS/Sham treatment. Since PCS will be assessed in all visits, we can trace the PCS change across the entire treatment course. Of course, the most important comparison will be the PCS between 1-week post-treatment follow-up (Visit 15) and the baseline (Visit 2) exams. Again, two-factor mixed-design repeated measures ANOVA with covariates will be used to: assess the within-subject significance of the PCS changes between pre- and post-treatment exams; and 2) to assess the between-group treatment effect by comparing IASIS with Sham. The dependent variables at both time points are PCS scores, and the predictors are time (pre- and post-treatment), group (IASIS versus Sham), and their interaction. We predict that compared with the sham group, mTBI Veterans received IASIS treatment will show significantly greater decreases in PCS symptoms between baseline and post-treatment assessments (Hypothesis 4). The preliminary result in C.6.1 (Fig. 6A) supports this hypothesis.

Besides RPQ and NSI, we will use the same statistical approach to examine IASIS-related changes in additional symptom measures: CAPS-5 and PCL-5 for PTSD symptoms, PSQI for sleep problems, and MGPQ for pain. Since brain injury increases the likelihood of both PCS and PTSD, we hypothesize that by treating the mTBI aspect using IASIS in Veterans, PCS will improve, and that PTSD symptoms will be reduced as well (Hypothesis 5, C.6.1), consistent with a model in which TBI impairs functioning of prefrontocortical and networked systems that are believed to be integral for inhibiting fear responses and promoting fear extinction [26,79]. False discovery rate (FDR) will be used to correct family-wise error [85].

D.6 Correlating IASIS Related Changes in MEG with Symptoms and Neuropsychological Exams (Aim 3)

Correlating IASIS-related changes in MEG slow-wave source imaging and PCS in mTBI: Correlation analyses will be performed to examine the neuronal correlates of changes in MEG slow-wave generation and PCS scores in Veterans with mTBI in both IASIS and Sham groups. Specifically, we will correlate the changes in the total abnormal MEG Z-scores as well as voxel-wise Z-score MEG source imaging measures with changes in PCS due to IASIS treatment, by comparing PCS scores from post-treatment follow-up (Visit 15) with the baseline (Visit 2) exams. We predict that reduction in MEG slow-wave generation will correlate with reduced total PCS score as well as specific symptom scores (e.g., sleep disturbance, post-traumatic headache, photophobia, and memory problem symptoms) (Hypothesis 6). The voxel-wise analysis may provide important spatial information of the slow-wave generation related to each PCS category. Linear regression analyses will be performed for the correlation analysis, and FDR will be used to control family-wise error [85] using correct $q < .05$. We predict that in mTBI-IASIS group, but on

in the sham group, reduction in MEG slow-wave generation will correlate with reduced symptoms. Preliminary data presented in Section C.6.2 and Fig. 6C support this hypothesis.

Correlating IASIS-related changes in MEG slow-wave source imaging and cognitive functions in mTBI: We will study the relationship between changes in MEG slow-wave generation with those in neuropsychological exam scores between post-IASIS (Visit 15) and baseline exams (Visit 2). For neuropsychological tests that differentiate HC and mTBI groups, we will perform linear regression analysis, where treatment-related changes

in neuropsychological test scores are used to predict the changes in MEG measures including voxel-wise slowwave Z-score (FDR corrected for family-wise error) and the total abnormal MEG Z-scores. We also predict that in mTBI-IASIS group, but not in the sham group, reduction in MEG slow-wave generation will correlate with improvement in the different cognitive domains that govern functioning.

D.7 Examining the effects of Covariate Variables on IASIS treatment and Exploratory Analyses in mTBI

Covariate variables to be included in above statistical analysis: Age, gender, education, combat exposure (DRRI-2), socioeconomics, OSU TBI-ID for lifetime history of TBI, ASSIST and AUDIT for alcohol and substance uses, and order of mTBI to PTSD will be added as covariates in the linear regression and ANOVA analyses in Sections D.4 - D.6. However, since these variables will be matched during our group assignment, we do not predict they will have major impact to the results of statistical analyses.

Exploratory studies: We will add 10 minutes rs-fMRI in Visit 2 to our existing MRI acquisition on a 3T system in the two mTBI groups, and use the data for exploratory FC analyses of the relationship between rsfMRI and rs-MEG using the approach described in [14]. We will also add an N-back MEG task in Visits 2 and 15 for exploratory analyses of changes in working memory function due to IASIS treatment. We have previously found that changes in rs-MEG neural patterns are highly associated with the working memory performance of the N-back MEG task [110].

D.8 Description and Justifications of Sampling Plan, Power Analysis, and Time Table

For assessing the specificity (1- false-positive rate) of the MEG slow-wave measures on a single-subject basis, the number of HC subjects in the normative database has to be sufficiently large. N=75 will allow us to reliably assess the normative datasets from HC participants. By choosing K=3 in the K-fold cross-validation approach, 2/3 (N=50) will be used to construct the normative database and the remaining 1/3 (N=25) to test the specificity, with reliable performance.

Power analysis: We don't expect that one set of sample sizes will meet the needs of all 3 aims and 6 hypotheses equally well. Hence, for a proposed set of sample sizes, some hypotheses may be overpowered whereas the others may be adequately powered. We used G*Power (University of Dusseldorf) for the power analysis. The power analyses below show that the N=50 in each of the two mTBI groups (i.e., mTBI-IASIS and mTBI-Sham) provides a good balance for all the hypotheses. For Hypothesis 1, our voxel-wise MEG slowwave source imaging is expected to show substantially higher sensitivity in detecting in mTBI groups than conventional MRI. Based on our preliminary data using McNemar's test in C.2, we expect a large effective size (odds ratio > 50). At two-tailed, $\alpha=0.01$, N=50 in each of the mTBI groups, the estimated power is > 0.98. We also predict high test-retest reliability of MEG slow-wave source imaging measures in N=100 Veterans (50 in each group) that will have two consecutive MEG exams (Visits 2 and 3). Based on our preliminary data in C.4, high level of test-retest reliability (i.e., ICCs ≥ 0.75) is expected in our rs-MEG slow-wave source imaging. In Hypothesis 2, we predict that IASIS treatment will enhance neural healing by initially potentiating slow-wave generation immediately after each treatment session. In Hypothesis 3, we expect that in Veterans in mTBI-IASIS group, but not in mTBI-Sham group, MEG source imaging (voxel-wise and total Z-score) will ultimately show a significant decrease in abnormal slow-waves between pre- and post-treatment exams. Based on preliminary data in C.5 and C.6 (Figs. 6B and 7), for Hypotheses 2 and 3, we expect large effect size (Cohen's $f>0.45$). At two-tailed, $\alpha=0.01$, N=50 in each of the mTBI groups, the estimated power is > 0.98. In Hypotheses 4 and 5, we predict that, compared with the sham group, mTBI participants in the IASIS treatment group will show significantly larger decreases in PCS and PTSD symptoms between baseline and post-treatment assessments. Based on pilot data in C.6 and information from [68], we expect medium-to-large effective size for total the RPQ (Cohen's $f>0.38$) and medium-to-large effective size for PCL (Cohen's $f>0.32$). At two-tailed, $\alpha=0.01$, N=50 in each of the mTBI groups, the estimated power is > 0.95 for total RPQ score, and power > 0.85 for PCL. We will also have power > 0.88 for 5 individual PCS scores (e.g., PSQI for sleep problems, MGPQ for pain, etc.) with the conservative Bonferroni correction. For Hypothesis 6, we expect changes in MEG slowwaves will correlate with PCS scores and cognitive deficits in specific domains in mTBI groups due to IASIS. Based on our preliminary data in C.6 and C.7, we expect medium-to-large effect sizes ($|r| \sim 0.4-0.8$). With N=50 in each mTBI group, two-tailed, $\alpha=0.05$, the estimated powers are > 0.85 for changes in MEG slow-wave correlating with total PCS score or one NP variable. The same level of power can be achieved for 5 symptom individual PCS / NP variables at $\alpha=0.05$, in the conservative case of Bonferroni correction, and for more than 5

neuropsychological / symptom variables when using FDR correction. **Time Table of Tasks: See attachment.**

D.9 Combining data from pilot study, H150047

In order to complete data analysis with a larger sample size, we plan to combine data from pilot study H150047 for future analysis and publications. The data that will be combined will only be de-identified data from neuropsychological testing, IASIS treatments, MEG sessions, and MRI scans, using study numbers. Participants from this pilot study will not be re-consented and no waivers or consent or authorization will be needed in order to use the previously collected de-identified data.

Phase Orange COVID-19 Adoptions:

In compliance with VASDHS Policy, in-person interaction with research subjects during the COVID-19 pandemic, Phase Orange, will be limited to activities only viable if conducted in-person. Data collected in-person will be limited to consenting, MEG and MRI scan sessions, as well as IASIS, Nexalin, and/or TUNS treatments. Other aspects of participation, to include questionnaires, clinical interviews, and neuropsychological tests not requiring in-person interaction may be conducted remotely via phone. If appropriate or preferred by volunteers, forms, questionnaires, clinical interviews, and neuropsychological testing can be conducted in a private room, or outside (e.g., car, etc.) when performed in conjunction with an in-person study session, or in a testing room with appropriate social distancing, personal protective equipment (PPE), and sneeze guards. These adaptions will not change the data collected by this study (aside from the temporary removal of the TOMM, DEKFS Trail-making, WAIS-IV Symbol Search, WASI Matrix, DKEFS Color Word Interference, and WAIS-IV Digit Symbol Coding the neuropsychological testing battery due to concerns over shared surfaces and materials if neuropsychological testing was collected over the phone), and will allow the study to operate in full compliance of Phase Orange guidelines.

Section 9.4 Devices

9.4) For each research device, state the status of the device, the PI's determination as to whether the device is a significant or non-significant risk device, and provide justification for this determination. A copy of determinations from the FDA should be attached. - Also, for investigational devices describe how and by whom the device will be received, stored, secured and dispensed.

Device Classification Name: Device, Biofeedback
510(K) Number: K971708

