We propose to study a total of 175 subjects in three groups. Two groups contain OEF/OIF/OND Veterans (age 18-60) diagnosed with chronic mTBI with persistent PCS (majority due to blast). Participants in these two groups will be matched on age, gender, education, combat exposure, symptom chronicity, and socioeconomic status. Group 1 (mTBI-IASIS group, N=50) contains mTBI Veterans to be blindly assigned to a 6-weeks IASIS treatment with two sessions per week. Group 2 (mTBI sham group, N=50) contains mTBI Veterans to be blindly assigned to a sham treatment for 6 weeks with also two sessions per week. Veterans with mTBI in both Groups 1 and 2 must currently have persistent PCS at least 6 months post injury (i.e., the most recent injury). In addition, PTSD symptoms will be assessed and matched in symptom severity and diagnostic category in the two mTBI groups. Group 3 (control group, N=75): age-, gender-, education-, combat exposure-, and socioeconomically-matched HC Veterans.

The above table and Fig. 10 shows the study flow chart with 16 visits. After consent, Visit 1 for all three groups will include baseline neuropsychological (NP) and mental health assessment (MHA). Then, baseline rs- MEG and MRI scans will be performed in Visit 2 for all participants. The rs-MEG data from the HC group will be used to establish a normative HC database. Next, a re-test rs-MEG exam will be performed in a subset of HC participants (N=25, green dashed line) at Visit

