D.1.2. Exclusion criteria for study participations include: 1) history of other neurological, developmental, or psychiatric disorders (based on the DSM-5 (MINI-7) [86] structured interview), e.g., brain tumor, stroke, epilepsy, Alzheimer's disease, schizophrenia, bipolar disorder, ADHD, or other chronic neurovascular diseases such as hypertension and diabetes; 2) substance or alcohol use disorders according to DSM-5 [87] criteria within the six months prior to the study; 3) history of metabolic or other diseases known to affect the central nervous system (see [88] for similar criteria); 4) Metal objects (e.g., shrapnel or metal fragments) that fail MRI screening, or extensive metal dental hardware (e.g., braces and large metal dentures; fillings are acceptable) or other metal objects in the head, neck, or face areas that cause non-removable artifacts in the MEG data; 5)

Potential subjects will be administered the Beck Depression Inventory (BDI-II) to evaluate level of depressive symptoms, and suicidal ideation; any participant who reports a "2" or "3" on the BDI-II: item 9 (suicidal thoughts or wishes) will also be excluded. However, depression following mTBI or traumatic event of PTSD is common [89]; therefore, in two mTBI groups, we will include and match patients with depression symptoms reported after their injury/event, and will co-vary BDI-II score in data analyses.

D.1.3. Inclusion for the mTBI groups: All symptomatic mTBI patients will be evaluated in a clinical interview to document the nature of the injuries and ongoing PCS. The diagnosis of mTBI patients is based on standard VA/DOD diagnostic criteria. Inclusion in the mTBI patient group requires a TBI that meets the following criteria: 1) a loss of consciousness (LOC) < 30 minutes or transient confusion, disorientation, or impaired consciousness immediately after the trauma; 2) post-traumatic amnesia (PTA) < 24 hours; 3) an initial Glasgow Coma Scale (GCS) [90] between 13-15 (if available). Since the GCS assessment is often not available in theater, Veterans with missing GCS, but who meet other inclusion criteria will also be recruited. Each patient must have at least 3 items of persistent PCS (see below) at the beginning of the study.

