- Provide inclusion and exclusion criteria as appropriate. Provide a statement how non pregnancy is confirmed if pregnancy is an exclusion criteria.
- For multisite studies, provide the total number of subjects from all sites and include description of the local site's role as a coordinating center if applicable.
- Indicate the number of VA participants to be studied.
- Indicate the estimated number of consented subjects that will fail the screening process, if any.

Inclusion Criteria:

175 subjects in three groups: Two groups contain OEF/OIF/OND Veterans (age 18-60) diagnosed with chronic mTBI with persistent PCS (majority due to blast). Veterans in these two groups will be matched on age, gender, education, combat exposure, symptom chronicity, and socioeconomic status. Group 1 (mTBI-IASIS group, N=50) contains mTBI Veterans to be blindly assigned to a 6-weeks IASIS treatment with two sessions per week. Group 2 (mTBI sham group, N=50) contains mTBI Veterans to be blindly assigned to a sham treatment for 6 weeks with also two sessions per week. Veterans with mTBI in both Groups 1 and 2 must currently have persistent PCS at least 6 months post injury (i.e., the most recent injury). In addition, PTSD symptoms will be assessed and matched in symptom severity and diagnostic category in the two mTBI groups. Group 3 (control group, N=75): age-, gender-, education-, combat exposure-, and socioeconomically-matched HC Veterans. After completing 6 weeks of IASIS treatment, any Veteran participants in Group 1 who still mention or complain of remaining PCS in their month follow-up phone interview will be offered Nexaline treatment at no cost to the participant.

Exclusion Criteria:

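### Allocation to IASIS or sham is not described, three matched factors are missing from the model, and baseline adjustment should be the main test if allocation was random

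*Combined protocol and SAP*

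**What the plan says.** **Assignment.** D.4.2 has one staff research associate (SRA #1) who "will assign a mTBI participant to either the mTBI-IASIS or the mTBI-Sham group, with an attached code from an existing IASIS code bank". A second associate (SRA #2), who does not know the group, enters the code, and the device loads the active or sham programme. D.1.1 and the inclusion criteria in Section 10 use the same wording: the IASIS group "contains mTBI Veterans to be blindly assigned to a 6-weeks IASIS treatment with two sessions per week" and the sham group "contains mTBI Veterans to be blindly assigned to a sham treatment for 6 weeks with also two sessions per week". The term is not defined.

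**Masking.** D.4.2 concludes that "both the participant and IASIS treatment operator (SRA #2) are blind to the group assignment during the study". Groups are revealed only after Visit 16.

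**Matching.** D.1.1 states: "Participants in these two groups will be matched on age, gender, education, combat exposure, symptom chronicity, and socioeconomic status". It adds that "PTSD symptoms will be assessed and matched in symptom severity and diagnostic category in the two mTBI groups". On depression, D.1.2 says "we will include and match patients with depression symptoms reported after their injury/event, and will co-vary BDI-II score". D.7 lists its covariates, ending with "lifetime history of TBI, ASSIST and AUDIT for alcohol and substance uses, and order of mTBI to PTSD will be added as covariates", and says that these variables are matched when groups are assigned.

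**Analysis.** D.4.3, D.4.4 and D.5 test IASIS against sham with a two-factor mixed-design repeated-measures ANOVA with covariates. The predictors are time, group and their interaction.

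**The concern.** Masking the participant and the operator controls expectation. It does not stop the person who assigns from foreseeing or choosing the next group. Matching at assignment needs each participant's profile, and the text names no algorithm, no unit of matching (pair, stratum or whole group) and no responsible person or program. A reader therefore cannot tell whether this is a randomised trial or a matched, non-randomised, sham-controlled comparison. Hypotheses 2 to 5 attribute between-arm differences to IASIS, and how far they can do so depends on the answer.

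The answer also bears on the analysis. If allocation was random, adjusting for the starting value is valid and uses the data better than the planned contrast. If it was not, change scores and baseline-adjusted scores are each open to bias, and three factors singled out for matching are missing from the adjustment.

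**Working it through.** **1. Allocation text.** The supplied sections contain no random sequence, blocks, strata, minimisation or concealment. Forms of the word random appear only for a type of noise stimulation (B.3), a prior Nexalin trial (C.8) and two reference titles. The study calls itself double-blind and placebo controlled. It does not say whether SRA #1 takes part in screening.

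**2. Matched factors against covariates.**
- Matched: 6 in the main D.1.1 list, 2 for PTSD (severity, category), 1 for depression (D.1.2) and 4 more in D.7 (lifetime TBI history, ASSIST, AUDIT, order of mTBI to PTSD). 6 + 2 + 1 + 4 = 13.
- Covariates: 9 in D.7 plus BDI-II from D.1.2 = 10.
- Missing: 13 − 10 = 3, namely symptom chronicity, PTSD severity and PTSD category.

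**3. How a covariate must enter.** Take two complete visits, group G and a baseline covariate X. With X as a main effect only, it adds the same amount at both visits, so the change is β + δG and X cancels. With X-by-time the change is β + δG + φX. A numerical check (100 simulated participants, random-intercept model) gave a time-by-group estimate of 0.22836 without X, 0.22836 with its main effect and 0.24959 with X-by-time. The plan does not say which form it intends.

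**4. The plan's own power.** D.8 gives f = 0.45, 0.38 and 0.32, N = 100, two-tailed alpha 0.01. With λ = f² × N × 2 / (1 + ρ) and ρ = 0.5 (assumed; none is given), λ = 27.0, 19.25 and 13.65. Power is 0.994, 0.959 and 0.855, against the stated bounds of 0.98, 0.95 and 0.85. These are met, and no stated figure is disputed. That formula is for the group effect averaged over visits, so it does not check the contrasts below.

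**5. Efficiency if allocation was random.** Unit-variance scores, 50 per arm, pre-post correlation r (assumed):
- SE of the change contrast = √(2(1 − r) × 2/50); at r = 0.5 this is 0.200.
- SE of the baseline-adjusted contrast = √((1 − r²) × 2/50); at r = 0.5 this is 0.173.
- The variance ratio is (1 + r)/2: 0.65, 0.75 and 0.85 at r = 0.3, 0.5 and 0.7.

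Simulated power at alpha 0.01 for an assumed 0.6 SD effect:

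| r | Change | Baseline-adjusted |
|---|---|---|
| 0.3 | 47% | 69% |
| 0.5 | 64–65% | 79% |
| 0.7 | 89% | 94% |

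Reading the plan's f as 2f raw-score SD, at r = 0.5 and by normal approximation: PCL (0.64 SD) 73% against 87%; RPQ (0.76 SD) 89% against 97%; Hypothesis 3 (0.90 SD) 97% against nearly 100%.

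**6. If allocation was not random.** Illustrations with no true effect, 50 per arm, alpha 0.01, r = 0.5 and a 0.3 SD gap. Gap and r are assumed, and none of this estimates the actual bias.
- Selection on the observed baseline score: change contrast 3.4% false positives, baseline-adjusted 1.0%. The change estimate is off by −0.15 SD.
- A stable severity gap at both visits: change 1.0%, baseline-adjusted 4.1%. The adjusted estimate is off by +0.15 SD.
- Selection on prognosis that baseline does not capture: 0.3/0.200 = 1.50 SE for change and 0.3/0.173 = 1.73 SE for baseline-adjusted, in the same direction. False positives are about 13% and 18%, and both tests agree in about 10%. For r from 0.3 to 0.7 false agreement runs from about 6% to 22%.

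The third case is not far-fetched: D.1.8 allows ongoing cognitive behavioural therapy and medication, and neither is in the D.7 list.

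**The case against.** **It is only an undescribed method.** An existing code bank is compatible with a concealed random list, and matching can be done by a minimisation program. Fig. 10, the attachments and the pages left out of the supplied text may hold the detail. This stands. A reader might infer that the study was not randomised, or that SRA #1 chose groups by looking at patients; the documents support neither. Section 12.1 has screeners use the criteria to place callers in a group, but this most naturally means mTBI or control. Recruitment and consent are not cleanly separate, since the principal investigator may be involved in both (Sections 11 and 12.1), but that does not show access to upcoming codes.

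**The planned contrast already contains baseline.** Correct: it is the first time point, and under random allocation the time-by-group test is valid. A reader might infer that the planned test is wrong; it is only less powerful.

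**Agreement of two analyses could serve as the safeguard.** It holds the error at 0.4% to 0.6% in the first two cases in step 6, because each leaves one analysis unbiased. It fails in the third, so it cannot be a decision rule.

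**Changing the main test now is late.** Visits stopped on 09/30/2022 (Section 20), and Section 27.2 describes a laptop in use for data analysis. This stands and has to be disclosed.

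**Conclusion.** The point holds in a limited form. The supplied text does not describe how participants were allocated or protected from selection at assignment; it does not show that selection occurred. Two analysis points are concrete. Three of the 13 matched factors are absent from the covariates. The between-arm contrast also gives up efficiency if allocation was random: about 64% against 79% power for an assumed 0.6 SD effect at r = 0.5, with a smaller loss at the larger effects that D.8 assumes. If allocation was not random, neither analysis is safe alone, and agreement between them can be false in about 6% to 22% of null trials for an assumed 0.3 SD uncaptured gap. All these rates rest on assumed gaps, effects and correlations that the documents do not give.

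**What to change.** 1. **Allocation.** From the code-bank records, establish how assignments were generated, how and by whom or what matching was done, and who could see upcoming codes. State this in D.4.2. Enrolment is closed (Section 11.1), so a method must not be written in after the fact. If there was no random element, report a non-randomised, matched, sham-controlled comparison and limit the causal claims for Hypotheses 2 to 5.
2. **Covariates.** Add symptom chronicity, PTSD severity and PTSD category to D.7 and keep BDI-II. Enter covariates with their time interaction, or as covariates in an ANCOVA. For Hypothesis 5, baseline PTSD severity is the outcome's own baseline.
3. **If random allocation is confirmed.** Make the baseline-adjusted Visit 15 contrast the main between-arm test for Hypotheses 3 to 5. For Hypothesis 2, adjust the post-session value for the pre-session value. Fix this before unblinded results are seen; otherwise label it post hoc and keep the planned contrast alongside.
4. **If it is not confirmed.** Show change-score and baseline-adjusted results side by side as a sensitivity display, with no claim resting on their agreement.

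The cost is retrieving records, a paragraph of text and a few model terms, with no new participants or visits. Even charging one degree of freedom for each of the 13 factors (98 − 13 = 85), the two-sided 1% critical t moves only from 2.627 to 2.635. The real downsides are a possibly weaker causal label and a late change to the main test that must be disclosed.
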